## 2. INTRODUCTION

Dacomitinib (PF-00299804) is a selective, adenosine triphosphate (ATP) competitive, irreversible, small-molecule inhibitor of the HER (ERBB) family of receptor tyrosine kinases (RTKs), including the epidermal growth factor receptor (EGFR, HER1), the HER2 receptor (ERBB2), the HER4 receptor (ERBB4), and their oncogenic variants (eg, EGFR with del exon 19 or L858R mutations). It is currently approved for the first-line treatment of patients with locally advanced or metastatic non-small cell lung cancer (NSCLC) with EGFR-activating mutations.

### 2.1. Study Rationale

The primary metabolic pathways for dacomitinib in human liver microsomes and human hepatocytes in vitro are comprised of oxidation and glutathione conjugation. In vitro studies with human liver microsomes and recombinant cytochrome P450 (CYP) (rCYP) enzymes indicated that the formation of PF-05199265 (O-desmethyl dacomitinib) was mediated primarily by CYP2D6, while CYP3A was involved in the formation of other minor oxidative metabolites observed in humans following oral administration of a single dose of [C]dacomitinib.

In the absorption, distribution, metabolism, and excretion (ADME) study in humans (Study A7471020), following oral administration of a single [C]dacomitinib dose (45 mg, 100 µCi) to 6 male healthy participants, approximately 79% of the administered radioactive dose was recovered in feces (approximately 20% unchanged dacomitinib) and 3% in urine (<1% unchanged dacomitinib). Dacomitinib is orally bioavailable with mean absolute bioavailability of 80%. These data indicated significant hepatic component in the elimination of dacomitinib and minimal renal excretion of dacomitinib.

A dedicated hepatic impairment clinical study of dacomitinib (Study A7471018) in participants with mild or moderate hepatic impairment has been completed. Study A7471018 was a multi-center, Phase 1, open-label, non-randomized, single-dose, parallel group study conducted to evaluate the impact of mild hepatic impairment (Child-Pugh Class A) or moderate hepatic impairment (Child-Pugh Class B) on the pharmacokinetics (PK) of dacomitinib. In that study, a total of 25 men who had normal hepatic function (n = 8), mild hepatic impairment (n = 8), or moderate hepatic impairment (n = 9) but were otherwise healthy were enrolled and received a single 30 mg dose of dacomitinib following an overnight fasting for at least 8 hours. Results demonstrated that plasma dacomitinib area under the concentration time curve from time 0 to infinity ( $AUC_{inf}$ ) and maximum observed plasma concentration ( $C_{max}$ ) were similar in participants with mild hepatic impairment and were reduced marginally (by 15% and 20% for  $AUC_{inf}$  and  $C_{max}$ , respectively) for participants with moderate hepatic impairment relative to participants with normal hepatic function.

The effect of hepatic impairment on dacomitinib was further evaluated using the National Cancer Institute (NCI) hepatic impairment classification in a pooled population PK analysis of 1381 participants, which included 158 participants with mild hepatic impairment (total bilirubin  $\leq$  upper limit of normal [ULN] and aspartate transaminase [AST]  $>$  ULN, or total bilirubin  $>1$  to  $1.5 \times$  ULN with any AST), 5 participants with moderate hepatic impairment (total bilirubin  $>1.5$  to  $3 \times$  ULN and any AST) and 1 participant with severe hepatic impairment (total bilirubin  $> 3 \times$  ULN and any AST). Limited data (n=1) were available for severe hepatic impairment. Participants with mild hepatic impairment had similar dacomitinib clearance (CL) compared to participants with normal hepatic function. Dacomitinib CL was higher in participants with moderate hepatic impairment with mean CL of 31.4 L/h (n=5) compared to 20.5 L/h (n=1202) in participants with normal hepatic function. Hepatic function was not a significant covariate on dacomitinib CL.

Based on the results from both the formal hepatic impairment Study A7471018 and the pooled population PK analysis, mild or moderate hepatic impairment is considered to not have a clinically relevant effect on dacomitinib PK. Therefore, no dose adjustment of dacomitinib is recommended in patients with mild or moderate hepatic impairment. Insufficient data are however available regarding the use of dacomitinib in patients with severe hepatic impairment to provide dosing recommendations in this patient population.

The purpose of this study is to evaluate the effect of severe hepatic impairment on the single dose PK of dacomitinib.

## **2.2. Background**

### **2.2.1. Nonclinical Pharmacology**

Dacomitinib is a highly selective irreversible small molecule inhibitor of the HER (human epidermal growth factor receptor) family of tyrosine kinases. The  $IC_{50}$  values against the human catalytic domains of HER-1, HER-2, and HER-4 (HER-3 does not possess tyrosine kinase activity) are 2.8 ng/mL (6.0 nM), 21.5 ng/mL (45.7 nM) and 34.7 ng/mL (74 nM), respectively. Dacomitinib is  $>500 \times$  selective relative to the concentrations required to inhibit the janus kinase 3 (JAK3), protein kinase b (Akt), insulin-like growth factor 1 receptor (IGF1R), and the platelet-derived growth factor receptor (PDGFR) in kinase assays. The  $IC_{50}$  values are 1676,  $>18,800$ ,  $>18,800$ , and 6298 ng/mL (3566,  $>40,000$ ,  $>40,000$ , and 13,400 nM), respectively. Dacomitinib inhibits the tyrosine kinase activity of the HER family through binding at the ATP binding site, which results in covalent modification of a cysteine in the ATP binding pocket. Dacomitinib exhibited anti-tumor effects in 4 different human xenograft models that express and/or overexpress HER family members. In these xenograft models, the therapeutic activity ranged from complete regression to delayed progression. The inhibitory effects on tumor growth generally lasted throughout compound administration. An active metabolite, PF-05199265, has been identified which has similar inhibitory and selectivity profiles compared to dacomitinib.

### **2.2.2. Nonclinical Pharmacokinetics and Metabolism**

In nonclinical species (rats, dogs, and monkeys), dacomitinib exhibited moderate to high total plasma clearance in relation to hepatic blood flow, high volume of distribution, and moderate to high oral bioavailability ranging from 56% to 109%. Ratios of the AUC from time 0 to 24 hours postdose (AUC24) for PF-05199265, a circulating active metabolite in humans, to parent were 0.18 in rats and 1.9 in dogs after oral administration of dacomitinib for 3 days. In toxicokinetic studies with rats, rabbits, and dogs, systemic exposure of dacomitinib generally increased with increasing of dose within the dose ranges examined.

After oral administration, [C]dacomitinib undergoes oxidation and glutathione conjugation as the primary metabolic pathways in rats, dogs, and humans. Formation of PF-05199265 is mediated primarily by CYP2D6 and to a lesser extent, by CYP2C9. CYP3A4 contributes to the metabolism of dacomitinib in the formation of other minor oxidative metabolites. The route of excretion of radioactivity in rats, dogs, and humans was primarily via feces.

Dacomitinib and PF-05199265 demonstrated little or no inhibition of CYP1A2, CYP2B6, CYP2C8, CYP2C9, CYP2C19, or CYP3A activities in human liver microsomes. However, dacomitinib and PF-05199265 inhibited CYP2D6 activity, and may have the potential for clinically relevant drug-drug interaction (DDI) with concomitantly administered CYP2D6 substrates. No significant induction of CYP3A, CYP1A2 or CYP2B6 in cryopreserved human hepatocytes was observed. Based on in vitro data, dacomitinib may have the potential to inhibit uridine-diphosphate glucuronosyltransferase (UGT)1A1 activity.

Dacomitinib has a low potential to cause DDI by inhibiting the efflux transporters P-glycoprotein (P-gp) systemically, organic anion transporting polypeptides (OATP)1B1, OATP1B3, organic anion transporter (OAT)1, OAT3, organic cation transporter (OCT)2, and human bile salt export pump (BSEP). However, dacomitinib may have the potential to inhibit breast cancer resistance protein (BCRP), P-gp in the gastrointestinal (GI) tract, and OCT1.

### **2.2.3. Nonclinical Safety**

Dacomitinib was assessed in a series of nonclinical studies that included repeated-dose toxicity studies in rats and dogs up to 6 or 9 months in duration, respectively, and safety pharmacology, genotoxicity, and reproductive embryo-fetal development studies. Based on the nonclinical studies conducted, the kidney, digestive system, epithelial cells, and liver have been identified as the primary target tissues/organs of toxicity. Based on the results of the genotoxicity assays conducted, dacomitinib would not be expected to pose a genetic risk for acute or chronic dosing in humans. Embryo-fetal development studies were performed in rats and rabbits where the effects were limited to reductions in maternal and fetal body weight, and lower maternal food consumption. There was no teratogenicity, mortality, or moribundity detected at any dose level tested.

#### 2.2.4. Clinical Overview

As of 29 July 2016, 3182 patients have been treated in 17 clinical studies and 143 healthy participants and 15 patients with solid tumors have been treated in 9 clinical pharmacology studies. Dacomitinib was administered to 2148 of the patients in these trials, in 1975 patients as a single agent or in combination with figitumumab (CP-751,871, a monoclonal antibody targeting the IGF1R), crizotinib (an anaplastic lymphoma kinase [ALK], mesenchymal-epithelial transition [MET] and c-ROS oncogene 1 [ROS1] tyrosine kinase inhibitor), or gedatolisib (PF-05212384, a phosphoinositide 3-kinase [PI3K]/mTOR inhibitor), and in 173 patients in Phase 1 combination therapy studies. Most patients treated in clinical studies had locally advanced or metastatic NSCLC. There were 1473 patients with NSCLC who received single-agent dacomitinib 45 mg once daily (QD), the maximum tolerated dose as determined by Studies A7471001, A7471003, and A7471005. Of these patients, 394 patients had NSCLC with EGFR-activating mutations; 255 of these patients received dacomitinib as first-line treatment.

The most frequently reported adverse events (AEs) in  $\geq 10\%$  of patients included GI-related, skin-and-nail-related, respiratory, and constitutional events.

Results from Study A7471015 indicated that dacomitinib can be administered with or without food. Following a single oral administration of dacomitinib at 45 mg in patients with advanced malignant solid tumors, the median time to reach the maximum observed plasma concentration ( $T_{max}$ ) of dacomitinib occurred approximately at 5 to 6 hours after dosing. Dacomitinib underwent extensive extravascular distribution with a geometric mean apparent volume of distribution ( $V_z/F$ ) ranging from 2424 to 2537 L/h and had a mean apparent terminal plasma half-life ( $t_{1/2}$ ) ranging from 54 to 80 hours. Following administration of multiple daily doses of dacomitinib at 45 mg to patients with advanced malignant solid tumors, steady-state was reached within 14 days, accumulation of dacomitinib in patients ranged from 5.0 to 6.4-fold for AUC, reflecting the observed long  $t_{1/2}$ . The geometric AUC over dosing interval ( $AUC_{tau}$ ) and  $C_{max}$  of dacomitinib at steady-state ranged from 1621 to 2213 ng•h/mL and 79.5 to 108.0 ng/mL, respectively. Plasma exposure of dacomitinib increased proportionally with dose in the dose range of 2 mg to 60 mg, indicating linear PK.

Dacomitinib undergoes oxidative metabolism and glutathione conjugation. Oxidative metabolism of dacomitinib involves CYP2D6 for the formation of O-desmethyl dacomitinib (PF-05199265) and CYP3A for the formation of other minor oxidative metabolites. The O-desmethyl metabolite, PF-05199265, is also a potent inhibitor of the HER kinase family in vitro. However, the steady-state exposure of PF-05199265 in human plasma is  $<20\%$  when compared with the exposure observed for dacomitinib. Furthermore, PF-05199265 is also highly bound to plasma proteins ( $>99\%$ ), which indicates that the unbound fraction for PF-05199265 in plasma is  $<1\%$  of the reported total plasma exposure.

A dedicated hepatic impairment study (Study A7471018) was conducted to evaluate the effect of hepatic impairment on dacomitinib exposure after a single 30 mg dose. This was a Phase 1 open-label, non-randomized, single-dose, parallel-group study in 25 participants with mild hepatic impairment (Child-Pugh Class A, score 5-6,  $n = 8$ ), moderate hepatic

impairment (Child-Pugh Class B, score 7-9, n = 9), and a control group of healthy participants with normal hepatic function (n = 8). The results showed that the mean fraction of dacomitinib unbound in plasma ( $f_u$ ) was identical across the 3 groups ( $f_u = 0.02$ ). The mean (percent coefficient of variation [%CV])  $f_u$  of PF-05199265 was 0.00011 (28%), 0.00016 (69%), and 0.00025 (62%) for participants with normal hepatic function, mild hepatic impairment, and moderate hepatic impairment, respectively. Results also showed that mild hepatic impairment status did not alter dacomitinib plasma exposures and that moderate hepatic impairment status reduced dacomitinib plasma exposures ( $AUC_{inf}$  and  $C_{max}$  by 15% and 20%, respectively) as compared to normal hepatic function. These changes are not considered clinically significant and no starting-dose adjustment is currently recommended for patients with mild or moderate hepatic impairment. In addition, a single oral 30 mg dose of dacomitinib was well tolerated in participants with mild or moderate impaired hepatic function. No participants in the normal hepatic function group or the mild hepatic impairment group experienced an AE. One (1) participant in the moderate hepatic impairment group died due to a road traffic accident. This death was classified as a serious adverse event (SAE) and was considered to be severe but was not treatment-related. There were no laboratory safety tests, vital signs results, or electrocardiogram (ECG) results of clinical concern.

### **2.3. Benefit/Risk Assessment**

Dacomitinib is not expected to provide any clinical benefit to the participants of this study. This study is designed to evaluate safety, tolerability, and PK in participants with severe hepatic impairment and matched controls to assist the further clinical development of dacomitinib.

More detailed information about the known and expected benefits and risks and reasonably expected AEs of dacomitinib may be found in the investigator's brochure (IB), which is the single reference safety document (SRSD) for this study.

### 3. OBJECTIVES AND ENDPOINTS

Objectives	Endpoints
Primary:	Primary:

 
To evaluate the effect of severe hepatic impairment on the single dose plasma PK of dacomitinib.
 
	
 
Plasma <math>C_{max}</math> and <math>AUC_{inf}</math> of dacomitinib. If <math>AUC_{inf}</math> cannot be reliably estimated, then AUC from time 0 to the time of last quantifiable concentration (<math>AUC_{last}</math>) will be used as the primary endpoint.
 

Secondary:	Secondary:

 
To assess the safety and tolerability of a single oral dose of dacomitinib in participants with normal hepatic function and participants with severe hepatic impairment.
 
	
 
Overall safety profile as characterized by laboratory test abnormalities, physical examination, vital signs, ECGs, and AE monitoring.
 

Tertiary/Exploratory:	Tertiary/Exploratory:

 
To characterize the effect of severe hepatic impairment on other plasma PK parameters of dacomitinib and its metabolite PF-05199265.
 
	
 
Plasma <math>AUC_{last}</math>, apparent oral clearance (<math>CL/F</math>), <math>V_z/F</math>, <math>t_{1/2}</math>, <math>T_{max}</math>, <math>f_u</math>, unbound <math>AUC_{inf}</math> (<math>AUC_{inf,u}</math>), unbound <math>AUC_{last}</math> (<math>AUC_{last,u}</math>), unbound <math>C_{max}</math> (<math>C_{max,u}</math>), unbound <math>CL/F</math> (<math>CL_u/F</math>) and unbound <math>V_z/F</math> (<math>V_{z,u}/F</math>) for dacomitinib; <math>C_{max}</math>, <math>AUC_{inf}</math>, <math>AUC_{last}</math>, <math>t_{1/2}</math>, <math>T_{max}</math>, <math>f_u</math>, <math>AUC_{inf,u}</math>, <math>AUC_{last,u}</math>, <math>C_{max,u}</math> for PF-05199265, as data permit.
 

 
To analyze CYP2D6 genotype in pharmacogenetic samples.
 
	
 
CYP2D6 phenotype.
 

 
To enable exploratory research through collection of banked biospecimens, unless prohibited by local regulations or ethics committee decision.
 
	
 
Potential results from exploratory analysis of banked biospecimens (these results may or may not be generated in the context of the present study).
 

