#### **4.2. Scientific Rationale for Study Design**

A parallel group design will be utilized to compare the dacomitinib PK between participants with normal hepatic function and participants with severely impaired hepatic function but are otherwise healthy. The participants from the severely impaired hepatic function cohort will be recruited first, then the participants from the normal hepatic function cohort will be recruited later to match the median demographics from severe hepatic impairment group. The modified Child-Pugh classification system will be the method used in this study to identify participants with severe hepatic impairment. Additionally, total bilirubin and AST will be assessed in this study as per the recommendations of the National Cancer Institute Organ Dysfunction Working Group Criteria for assessment of hepatic impairment.

This study is designed using a single dose of dacomitinib considering that single dose plasma PK of dacomitinib has been documented to be generally predictive of exposure at steady state. All participants enrolled in this study will receive 1 single oral 30 mg dose of dacomitinib administered as tablet(s). The PK samples will be collected serially up to 264 hours postdose, which has been shown to be adequate for participants with normal, mild or moderate hepatic function. This sampling duration is also expected to be adequate for characterizing the elimination phase of the plasma dacomitinib concentration-time profile for participants with severe hepatic impairment, for whom the elimination half-life of dacomitinib may be prolonged.

Dacomitinib undergoes both oxidative metabolism and glutathione conjugation. Oxidative metabolism of dacomitinib involves CYP2D6 for the formation of major circulating metabolite, PF-05199265, which has similar in vitro pharmacological activities as dacomitinib. Therefore the plasma PK for both dacomitinib and PF-05199265 will be evaluated in this study.

Since CYP2D6 metabolism is a component of dacomitinib elimination, genetic polymorphisms of CYP2D6 may have the potential to alter dacomitinib PK. A 3-mL blood sample will be collected on Day -1 from each participant for genotyping CYP2D6 polymorphism. Only participants identified as an CYP2D6 extensive metabolizer (EM) or CYP2D6 intermediate metabolizer (IM) will be included in the primary statistical analysis to evaluate the impact of severe hepatic impairment on dacomitinib plasma PK.

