##### 9.4.3.1. Pharmacokinetic Analyses

The effect of hepatic impairment on PK parameters will be assessed by constructing 90% confidence intervals (CIs) around the estimated difference between the Test (severe hepatic impairment cohort; Cohort 1) and the Reference (normal hepatic function; Cohort 2) using a one-way analysis of variance (ANOVA) model based on natural log transformed data. Only participants with CYP2D6 EM and IM in each cohort will be included in this analysis.

One-way ANOVA will be used to compare the natural log transformed  $AUC_{inf}$ ,  $AUC_{last}$  and  $C_{max}$ , and  $AUC_{inf,u}$ ,  $AUC_{last,u}$  and  $C_{max,u}$  of dacomitinib and PF-05199265, as data permit, for severe hepatic impairment cohort (Test) to the normal hepatic function cohort (Reference). Estimates of the adjusted mean differences (Test-Reference) and corresponding 90% CIs will be obtained from the model. The adjusted mean differences and 90% CIs for the differences will be exponentiated to provide estimates of the ratio of adjusted geometric means (Test/Reference) and 90% CIs for the ratios as a percentage.

The dacomitinib PK parameters ( $AUC_{inf}$ ,  $AUC_{inf,u}$ ,  $AUC_{last}$ ,  $AUC_{last,u}$ ,  $C_{max}$ ,  $C_{max,u}$ ,  $T_{max}$ ,  $t_{1/2}$ ,  $CL/F$ ,  $CL_u/F$ ,  $V_z/F$ , and  $V_{z,u}/F$ ) and PF-05199265 PK parameters ( $AUC_{inf}$ ,  $AUC_{inf,u}$ ,  $AUC_{last}$ ,  $AUC_{last,u}$ ,  $C_{max}$ ,  $C_{max,u}$ ,  $T_{max}$ ,  $t_{1/2}$ ) will be summarized descriptively by cohort. Boxplots of mean, median and individual participant parameters will be made by cohort for  $AUC_{inf}$ ,  $AUC_{inf,u}$ ,  $AUC_{last}$ ,  $AUC_{last,u}$ ,  $C_{max}$ , and  $C_{max,u}$ . Similar presentations will also be made for other PK parameters, if considered relevant. Dacomitinib and PF-05199265 total and unbound concentrations will be listed and summarized descriptively by PK sampling time and cohort. Summary profiles (means and medians) of the dacomitinib and PF-05199265 concentration-time data will be plotted by cohort on linear and semi-log scale. Individual participant concentration time profiles will be also presented. For summary statistics and summary plots by sampling time, the nominal PK sampling time will be used, for individual participant plots by time, the actual PK sampling time will be used.

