**Table 2. Noncompartmental PK Parameters**

PK Parameter	Analysis Scale	Dacomitinib	PF-05199265
$AUC_{inf}^*$	ln	A, D	A, D
$AUC_{inf,u}^*$	ln	A, D	A, D
$AUC_{last}$	ln	A, D	A, D
$AUC_{last,u}$	ln	A, D	A, D
$C_{max}$	ln	A, D	A, D
$C_{max,u}$	ln	A, D	A, D
$T_{max}$	R	D	D
$t_{1/2}^*$	ln	D	D
$CL/F^*$	ln	D	-
$CL_u/F^*$	ln	D	-
$V_z/F^*$	ln	D	-
$V_{z,u}/F^*$	ln	D	-
Fu	R	D	D

Key: A=analyzed using statistical model, D=displayed with descriptive statistics, ln=natural-log transformed, R=raw (untransformed), u=unbound, \*=if data permits

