### 7.3. Pharmacokinetic Parameters

Actual PK sampling times will be used in the derivation of PK parameters.

If a PK parameter cannot be derived from a subject's concentration data, the parameter will be coded as NC (ie, not calculated). (Note that NC values will not be generated beyond the day that a subject discontinues).

In summary tables, statistics will be calculated by setting NC values to missing; and statistics will be presented for a particular hepatic function group with  $\geq 3$  evaluable measurements. For statistical analyses (ie, analysis of variance), PK parameters coded as NC will also be set to missing; and analyses will not be performed for a particular parameter if more than 50% of the data are NC.

If an individual subject has a known biased estimate of a PK parameter (due for example to an unexpected event such as vomiting before all the compound is adequately absorbed in the body), this will be footnoted in summary tables and will not be included in the calculation of summary statistics or statistical analyses.

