**Table 3. PK Parameters to be Summarized Descriptively by Group**

Parameter	Summary Statistics
$AUC_{inf}$ , $AUC_{inf,u}$ , $AUC_{last}$ , $AUC_{last,u}$ , $C_{max}$ , $C_{max,u}$ , $CL/F$ , $CL_u/F$ , $V_z/F$ , and $V_{z,u}/F$	N, arithmetic mean, median, cv%, standard deviation, minimum, maximum, geometric mean and geometric cv%.
$T_{max}$	N, median, minimum, maximum.
$t_{1/2}$ , $t_u$	N, arithmetic mean, median, cv%, standard deviation, minimum, maximum.

Supporting data from the estimation of  $t_{1/2}$  and  $AUC_{inf}$  will be listed by analyte and group: terminal phase rate constant ( $k_{el}$ ); goodness of fit statistic from the log-linear regression ( $r^2$ ); the percent of  $AUC_{inf}$  based on extrapolation ( $AUC_{extrap\%}$ ); and the first, last, and number of time points used in the estimation of  $k_{el}$ . This data may be included in the clinical study report.

Presentations for dacomitinib and PF-05199265 concentrations will include:

- a listing of all concentrations sorted by hepatic function group (present in heading), subject id and nominal time postdose. The concentration listing will also include the actual times. Deviations from the nominal time will be given in a separate listing.
- a summary of concentrations by hepatic function group and nominal time postdose, where the set of statistics will include n, mean, median, standard deviation, coefficient of variation (cv), minimum, maximum and the number of concentrations above the lower limit of quantification.
- median concentrations time plots (on both linear and semi-log scales) against nominal time postdose by hepatic function group (all hepatic function groups on the same plot per scale, based on the summary of concentrations by hepatic function group and time postdose).
- mean concentrations time plots (on both linear and semi-log scales) against nominal time postdose by hepatic function group (all hepatic function groups on the same plot per scale, based on the summary of concentrations by hepatic function group and time postdose).
- individual concentration time plots by hepatic function group (on both linear and semi-log scales) against actual time postdose (there will be separate spaghetti plots for each hepatic function group per scale).
- Box and whisker plots for individual subject parameters ( $AUC_{inf}$ ,  $AUC_{inf, u}$ ,  $AUC_{last}$ ,  $AUC_{last, u}$ ,  $C_{max}$ , and  $C_{max, u}$ ) by hepatic function group and overlaid with geometric means.

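### Does the undefined switch of the primary AUC from AUCinf to AUClast need a rule in the SAP?

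*Protocol*

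**What the plan says.** Protocol Section 3 makes plasma Cmax and AUCinf of dacomitinib primary. If AUCinf "cannot be reliably estimated, then AUC from time 0 to the time of last quantifiable concentration" becomes the primary AUC. No criterion is given, and no level (participant, cohort or study) at which it applies.

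The SAP does not label any AUC as primary and does not mention the switch. It contains the following:

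- **Table 2 (Section 6.3.1).** AUCinf and AUClast are both planned for the statistical model and for descriptive statistics. AUCinf, t1/2, CL/F, Vz/F and the unbound AUCinf, CL/F and Vz/F carry a mark meaning "if data permits".
- **ANOVA text (protocol 9.4.3.1, repeated in SAP 8.1).** AUCinf, AUClast, Cmax and their unbound forms "of dacomitinib and PF-05199265, as data permit, for severe hepatic impairment cohort (Test) to the normal hepatic function cohort (Reference") are compared on the log scale, with 90% CIs.
- **Section 7.3.** If a value cannot be derived, "the parameter will be coded as NC (ie, not calculated") and set to missing; "analyses will not be performed for a particular parameter if more than 50% of the data are NC".
- **Section 8.1.** The terminal rate constant, r-squared and the extrapolated percentage of AUCinf will be listed. On reporting, the text is "This data may be included in the clinical study report".

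Protocol 4.2 says that sampling to 264 h is "expected to be adequate for characterizing the elimination phase" in severe impairment, while describing this group as one "for whom the elimination half-life of dacomitinib may be prolonged".

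**The concern.** The protocol's test is reliability, and the SAP's only written test is derivability. A profile with a fitted terminal slope and a large extrapolated tail passes the second and may fail the first. The protocol would then allow AUClast to become primary while the SAP keeps AUCinf in the model.

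The timing adds to the worry. The study is open-label, and the sponsor reviews all Cohort 1 PK data before recruiting Cohort 2 (protocol 4.1), so an unwritten standard could be settled with data in hand. The choice would matter most if severe impairment slowed elimination. AUClast would then miss more of the exposure in Cohort 1 than in Cohort 2, and its ratio would usually be the smaller one. The study is meant to fill a gap in dosing information, so an understated exposure ratio presented alone as primary would be a fair complaint.

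**Working it through.** **1. How far apart could the two ratios be?**

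Inputs from the protocol: last sample at 264 h (Section 1.3); half-life 54 to 80 h in patients with solid tumours (Section 2.2.4). The protocol gives no half-life for Cohort 1 and no quantification limit. Assumptions: one compartment, clearance falls with volume unchanged (so AUCinf and half-life rise by the same factor), all samples quantifiable to 264 h.

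Share of AUCinf beyond 264 h: e(t1/2) = exp(−ln2 × 264 / t1/2).

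AUClast ratio ÷ AUCinf ratio = (1 − e(test)) / (1 − e(reference)).

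| Reference t1/2 | e(ref) | Cohort 1 ×1.5: e, factor | Cohort 1 ×2: e, factor |
|---|---|---|---|
| 54 h | 0.034 | 0.104, 0.927 | 0.184, 0.845 |
| 67 h | 0.065 | 0.162, 0.897 | 0.255, 0.797 |
| 80 h | 0.102 | 0.218, 0.871 | 0.319, 0.758 |

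Adding first-order absorption (ka 0.6/h, assumed) gives 0.926, 0.896, 0.870 at ×1.5 and 0.843, 0.795, 0.757 at ×2. A true AUCinf ratio of 2.0 would therefore appear as an AUClast ratio of about 2.0 × 0.843 = 1.69 (54 h) or 2.0 × 0.757 = 1.51 (80 h).

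With an unchanged half-life the factor is 1.00. At 0.8 times it is 1.02 to 1.05.

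The tail reaches 20% (an illustrative limit, not in the documents) at 264 × ln2 / ln5 = 113.7 h, which is 113.7/80 = 1.4 to 113.7/54 = 2.1 times the reference range.

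Two sensitivities:

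- **Accumulation.** The protocol's 5.0- to 6.4-fold accumulation implies an effective half-life of 75 to 98 h by the bolus formula 24 × ln2 / (−ln(1 − 1/R)), or 69 to 91 h with ka 0.6/h. At 91 h the factors are 0.85 (×1.5) and 0.73 (×2).
- **Quantification limit.** At an assumed 1 ng/mL, the factors at 54 h move to 0.979 and 0.892. At 2 ng/mL they reach 1.03 and 1.04, so the order can reverse.

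**2. Which results does the plan produce?**

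| Item | AUCinf | AUClast |
|---|---|---|
| ANOVA, ratio and 90% CI (Table 2; protocol 9.4.3.1; SAP 8.1) | yes | yes |
| Geometric mean and CV by group (Table 3) | yes | yes |
| Individual values listed (SAP 8.1) | yes | yes |
| Written rule for skipping the ANOVA (SAP 7.3) | more than 50% NC | more than 50% NC |

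The Table 2 mark sits on every parameter that needs a terminal slope. It is absent from those that do not: AUClast, Cmax, their unbound forms, Tmax and fu. It reads as a derivability note, which Section 7.3 makes operational, and not as a lower rank for AUCinf. The corresponding qualifier in the ANOVA text covers the whole list, AUClast and Cmax included.

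**3. Do the two documents conflict?**

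Protocol Section 9 lets the SAP add detail, but major changes to primary endpoint definitions need an amendment. SAP silence therefore leaves the protocol switch in force. SAP 7.3 decides which values enter the model; protocol Section 3 decides which AUC is called primary. Both can be followed at once.

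**The case for a change.** The strongest case is that an endpoint should not change on an unwritten standard after the data have been seen, and that a sentence in the SAP would cost almost nothing. Section 7.3 does not say whether the 50% rule is per cohort or pooled. If pooled, all 8 Cohort 1 values could be NC without exceeding it (8/16 = 50%; with 10 controls, 8/18 = 44%). The listing of extrapolated percentages may stay out of the report. In simulations with 8 per group and an assumed quantification limit of 0 or 1 ng/mL, the 90% CI for AUClast covered the true AUCinf ratio in only 39% to 84% of trials when half-life doubled.

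The missing definition stands. The rest carries less weight:

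- **Coverage.** The simulation scores an AUClast interval against a different quantity. Neither document says that interval estimates the AUCinf ratio, and the AUCinf interval is planned beside it.
- **Optional listing.** The extrapolated percentage is in essence 100 × (1 − AUClast/AUCinf) for each participant, and both values are listed.
- **Direction.** Prolongation is stated only as a possibility. Moderate impairment lowered AUCinf by 15% (protocol 2.1), and population clearance was higher, at 31.4 against 20.5 L/h. That comparison has only 5 moderate participants, and moderate results need not carry over to severe disease, so this tempers the concern without removing it.
- **A written limit is not automatically better.** Suppose values with over 20% extrapolated were dropped, clearance halved and CV were 30% (all assumed). The AUCinf ratio among those kept falls from 2.00 to about 1.64 (54 h) or 1.31 (80 h), against AUClast ratios of 1.68 and 1.52. Keeping all derivable values, as Section 7.3 does, avoids that selection.

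**Conclusion.** No change follows. This is missing detail that leaves the planned results intact. The reliability standard is undefined and the SAP does not restate the switch, but both AUC ratios are planned with 90% CIs and both parameters are summarised and listed. SAP Sections 4.1 and 4.2 set no hypothesis or decision rule, so no error rate or formal conclusion depends on which ratio is called primary.

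If half-life were prolonged 1.5 to 2 times, the two ratios would differ by about 7% to 24% (factors 0.93 down to 0.76) for reference half-lives of 54 to 80 h with nothing below quantification. That difference would be visible in the planned output. These figures rest on an assumed prolongation, unchanged volume and one-compartment kinetics; the documents give no Cohort 1 half-life and no quantification limit.

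The conclusion rests on reading the Table 2 mark as derivability, which fits the rows that carry it. It would weaken if analysts used that mark to leave out an AUCinf ratio that Section 7.3 allows.
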